There are clinical studies showing that albumin administration and repeated therapeutic ascites puncture are relatively safe and effective in cirrhosis patients with large amounts of ascites or refractory ascites.^{4,5,6} In cirrhosis patients with refractory ascites, puncture is usually performed using an 18G angiocatheter. However, with conventional methods, the catheter is pulled out during ascites drainage and re-puncture is frequently performed. In many cases, the continuation of the catheter is unstable because it is fixed using tape and gauze without a special fixing device. The carahox set is a medical device created to compensate for the instability of maintaining the catheter. This study aims to suggest a convenient and safe therapeutic ascites method for patients with refractory ascites cirrhosis by comparing the success rate, re-puncture rate and complications of ascites puncture using a traditional method and a new fixation device.

5. Research Hypothesis

In patients with refractory ascites, the ascites puncture method with a new fixation device will have a higher success rate than the existing vascular catheter puncture method.

6. Research Objective

1) Primary Purpose

Comparison of success rates of ascites puncture between palliative ascites and kara-hoc in patients with cirrhosis with refractory ascites2) 이차 목적

- a. Surgical complications
- b. Patient satisfaction
- c. Operator satisfaction
- d. Factor of successful puncture
- e. Number of re-puncture

7. Research Population

7-1. Target Disease

Liver cirrhosis with ascites

7-2. Inclusion Criteria)

If all of the conditions below are met

- 1) Adult men and women over the age of 19

- 2) Patient with pathological or clinical diagnosis of cirrhosis
- 3) Patients with Grade 2 or higher ascites as a complication due to portal hypertension
- 4) Patients who are symptomatic and need regular ascites puncture
- 5) Patients consenting to this study

7-3. Exclusion Criteria

If any of the following conditions apply

- 1) Patients with ascites due to peritoneal metastasis due to malignant tumor
- 2) Patients with high bleeding risk (PT INR>3, PLT<30,000/mm3) difficult to perform ascites
- 3) Hepatic encephalopathy or hepatic nephrotic syndrome
- 4) Severe cardiovascular disease, lung disease, or DIC
- 5) Paracentesis refusal
- 6) Patients with ascites control possible with diuretics
- 7) Pregnancy

7-4. Target number of cases and calculation basis

In a preliminary study conducted on 20 cirrhotic subjects, 12 cases of successful puncture for ascites using both Kara-hoc and conventional method were performed, 5 cases of success only with Kara-hoc, and only 1 case of success with conventional method, with a difference of 20%, and a total of 61 cases were required, and 80 cases were required when the drop-out rate of 30% was taken into account.

McNemar Test Analysis

Numeric Results for Two-Sided Test

Power	N	P10	P01	Difference (P10-P01)	Proportion Discordant	Odds Ratio	Alpha	Beta
0.80516	61	0.250	0.050	0.200	0.300	5.000	0.050	0.19484

References

- Schork, M. and Williams, G. 1980. 'Number of Observations Required for the Comparison of Two Correlated Proportions.' Communications in Statistics-Simula. Computa., B9(4), 349-357.

7-5. Research Subject Recruitment Plan

Registered patients are recruited for patients with cirrhosis who require therapeutic ascites puncture due to intractable ascites among patients with cirrhosis who have visited the gastroenterology department outpatient department, ward, and emergency room.

7-6 . Additional protection measures in case of inclusion of vulnerable research subjects

Vulnerable subjects, such as children, pregnant women, and patients with hepatic encephalopathy, who are likely to have difficulty obtaining informed consent due to cognitive decline, were excluded from the study.

8. Expected study period

[figure not shown]
From IRB approval date to December 31, 2022

9. Research method (including observation/inspection items)

This study is a multi-center, prospective, interventional study, in which subjects who meet the selection criteria are enrolled at each institution during the study period from the date of research approval. The diagnosis of liver cirrhosis of the subject is made when there is a clear liver surface nodule in the performed imaging test and the liver biopsy is F4 or the liver elasticity measurement method is 11 kPa or more. is based on Subjects should perform multiple puncture at least twice during the outpatient or hospitalization period, and perform Karahoc puncture and vascular catheter puncture once each, and the order is set at random. The standard for successful ascites puncture is set as 3L or more of drainage when performing one puncture, and re-puncture is judged when ascites does not drain from the beginning after catheter insertion or when it is drained to less than 1L due to lumen obstruction or catheter dislocation. do. HR and BP measurements (immediately before and after multiple puncture and drainage are completed) before and after ascites are performed to compare the incidence of complications that may occur in each of the multiple puncture methods.

- 1) Primary evaluation item: success of multiple puncture
- 2) Secondary evaluation items: Occurrence of surgical complications, patient satisfaction, operator satisfaction, number of re-punctures

[Figure 1] Study flow chart

10. Evaluation Criteria and Evaluation Method

- Multiple puncture success : Drainage of 3L or more per puncture
- Complications : Bleeding, hematoma, intestinal perforation, hypotension, etc.
- Patients satisfaction : Assessment with Visual Analogue Scale

- Operator satisfaction : Assessment with Visual Analogue Scale
- Re-puncture : When ascites does not drain from the beginning after catheter insertion, or when it drains less than 1 L due to lumen obstruction or catheter dislocation and requires re-puncture

11. Differences from conventional treatment and this study (standard treatment guideline description of the target disease)

Patients with intractable ascites who have severe abdominal distension and dyspnea are referred to in the medical guidelines to perform a mass ascites puncture. Ascites puncture using the Karahoc set is also different in that it uses an improved puncture device with an abdominal wall fixation device according to the general indications for mass ascites puncture.

12. Result Variable

Whether the plural puncture was successful

13. Safety Assessment

Measure the pulse rate and blood pressure before and after multiple puncture, and check the properties of the liquid drained immediately after puncture to check for bleeding or intestinal perforation.

14. Data and Statistical Analysis

Comparison of the success rate of ascites puncture using the conventional method and the Karahoc device is a procedure that is repeated once in the same patient, so the influence of other confounding variables can be excluded and analyzed using the McNemar test. Multivariate analysis is performed using logistic regression for factors involved in treatment success in the entire patient group. Patient and operator satisfaction is quantitatively measured using Visual Analogue Scale, and then the average value of satisfaction is compared through t-test.

15. Secruing research ethics

The procedures stipulated in this protocol will ensure that researchers comply with the fundamental spirit of the GCP and the Declaration of Helsinki in conducting, evaluating and recording the results of this study, and will be implemented in accordance with the KGCP, the Law on Bioethics and Safety and related regulations.

This research protocol and its changes, (subject written consent and) related to information provided to the subject, are submitted to the IRB of the conducting institution to obtain formal approval for the conduct of the study in accordance with domestic regulations, and the IRB for conducting the study. The study will not be conducted prior to receipt of the documentation relevant to the decision.

16. Matters concerning the protection of personal information of research subjects

In order to protect the information of the research subjects, unnecessary personal identifiers of the collected data are removed. In particular, in the case record, the patient's name, resident registration number, Chart No. etc. should not be recorded, and the identifier code linked to personal information is managed separately. In addition, when presenting research results, make sure to present them in a form that cannot confirm the identity of the individual.

17. Research subject information and consent form

This study is for patients with refractory ascites, and the names of all subjects are kept confidential and the subjects are identified during recording and evaluation by the number assigned in the study. Inform the study subjects that all research data will be stored on a computer and treated in strict confidentiality. The subject consent form that has been signed is kept by the research director. By signing this protocol, the principal investigator agrees to obtain informed consent from the research subjects participating in the study, and also to receive due diligence upon request.

18. 연구자료 관리 및 보관

Electronic document files will be stored by installing an appropriate firewall and setting a password, and the password should be changed periodically. In addition, the person who can access the research file should be limited to those who are registered in the research and have the right to access. Relevant records should be stored in a secure space with controlled access or in a file storage with a lock. The data collected in the clinical trial will be stored for 3 years from the study end date and then destroyed, and after the end date, these documents will be transferred to a designated place such as a document storage room to prevent damage or loss due to accidents.

19. Benefit and risk of study subjects

Based on this study, we aim to improve patients' symptoms and improve the quality of medical care by enabling a more practical and safe method of ascites puncture for patients in need of therapeutic ascites.

20. Compensation plan for research subjects (if there is no compensation, the relevant reason)

This study will comply with relevant laws and regulations and strictly conduct clinical trials in accordance with related literature, recommendations, and suggestions, and immediate medical management will be made for complications that occurred during the course of this study. However, since the puncture needle of the Karahox set uses the same formulation as the vascular catheter, general complications that may occur during the puncture process will be treated in the daily treatment area, so there is no separate compensation provision for this.

21. Confidentiality (including protection of personal information of research subjects) and record keeping

The personal information to be collected is gender, date of birth, height, weight, disease name, past medical history, and blood test findings, and sensitive information is not included in the personal information to be collected. The purpose of collecting and using the above items is for the academic purpose of analyzing all patients to find out what factors cause a significant difference during ascites puncture, and it is not used for any other purpose.

Clinical trial schedule

Observation and inspection items	Screening	Intervention	
	Session 0 ¹⁾	Session 1 ¹⁾	Session 2
Subject consent	●		
Basic information	●		
Physical Exam/Vital Signs	●	●	●
Laboratory test ⁷⁾			
Hematology test	●	●	●
Blood coagulation test	●	●	●

Serum biochemical test	●	●	●
Radiologic examination	●		
Inclusion/Exclusion criteria	●		
Randomization ²⁾		●	
Therapeutic ascites puncture		●	●
Confirmation of puncture success		●	●
Confirmation of stability (adverse reaction)		●	●

1) Session 0 and session1 can be identical

2) Randomization is performed if the selection/exclusion criteria are met after confirming the screening test results. If randomization is a kara-hoc set, session 1 uses a kara-hoc set, session 2 uses a vascular catheter, and if randomization is a vascular catheter, session 1 uses a vascular catheter and seesion 2 uses a kara-hoc set.

22. References

1. Iwakiri Y Pathophysiology of portal hypertension. *Clin Liver Dis.* 2014;18:281-291

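### Enrolling 80 does not cover 30% drop-out: it leaves 56 pairs, not the 61 required, and exact power falls from 80.5% to 76.2%

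*Combined protocol and SAP*

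**What the plan says.** Section 7-4 (Target number of cases and calculation basis) takes its inputs from a preliminary study of 20 patients: "5 cases of success only with Kara-hoc, and only 1 case of success with conventional method, with a difference of 20" percent. The output table, headed "McNemar Test Analysis" and "Numeric Results for Two-Sided Test", reads "0.80516 61 0.250 0.050 0.200 0.300 5.000 0.050 0.19484". In column order these are power, N, P10, P01, difference, proportion discordant, odds ratio, alpha and beta. The text then concludes that "a total of 61 cases were required, and 80 cases were required when the drop-out rate of 30% was taken into account". The inflation formula is not shown.

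Section 9 (Research method) makes the design paired within patient: each patient is to "perform Karahoc puncture and vascular catheter puncture once each, and the order is set at random". Section 14 (Data and Statistical Analysis) compares success rates within patient, saying that "the influence of other confounding variables can be excluded and analyzed using the McNemar test". It does not say whether the exact or an asymptotic McNemar test will be used. The documents describe no replacement of drop-outs and no way of analysing a patient with only one procedure.

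**The concern.** A drop-out allowance should be set so that the patients who remain after the expected loss are still enough for the analysis. Here they are not: 80 less 30% falls short of 61. The likely cause is a common slip, adding 30% to the number needed instead of dividing that number by the proportion expected to remain.

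The design makes this matter for the primary endpoint. A McNemar test needs both outcomes from the same patient, so someone lost before the second session supplies no pair. The 61-pair calculation also has no slack, since 61 is the smallest number that reaches 80% power on the plan's own method. Any shortfall therefore takes power below 80% on that method, while Section 7-4 tells the reader that 30% drop-out has been provided for.

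**Working it through.** **Inputs, all from Section 7-4.** P10 = 5/20 = 0.25 (success with the new device only); P01 = 1/20 = 0.05 (success with the conventional catheter only); proportion discordant = 0.25 + 0.05 = 0.30; alpha = 0.05, two-sided; 61 pairs; stated power 0.80516; drop-out 30%; enrolment 80.

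**Step 1: reproduce the stated power.** For the two-sided exact McNemar test, the number of discordant pairs M among N pairs is binomial (N, 0.30). Given M = m, the number favouring the new device is binomial (m, 0.25/0.30 = 0.8333). Unconditional power is

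Power(N) = Σ over m of P(M = m) × P(two-sided exact binomial p ≤ 0.05 | m, 0.8333).

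- N = 60: 0.79730
- N = 61: 0.80516, equal to the stated figure to five decimals

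This is therefore the calculation behind the table, and 61 is the smallest N with power of at least 80%.

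**Step 2: find how 80 was reached.**

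- 61 × (1 + 0.30) = 79.3, rounded up to 80: matches
- 61 / (1 − 0.30) = 87.14, rounded up to 88: does not match

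The multiplication by 1.3 is an inference, because the document shows no formula. Steps 3 to 5 do not depend on it.

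**Step 3: apply the plan's drop-out rate to its enrolment.** 80 × 0.30 = 24 lost and 80 × 0.70 = 56 pairs left, which is 61 − 56 = 5 fewer than required.

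**Step 4: power at 56 pairs, same method.** Power(56) = 0.76244. The loss is 0.80516 − 0.76244 = 0.043, or 4.3 percentage points. Type II error goes from 0.19484 to 1 − 0.76244 = 0.23756.

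**Step 5: the drop-out that 80 can absorb.** 80 − 61 = 19 losses, and 19/80 = 23.75%.

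**Step 6: sensitivity to the version of the test.** Section 14 names no version, so the same inputs were run under the usual alternatives.

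| Version | Power at 61 pairs | Power at 56 pairs |
|---|---|---|
| Exact (reproduces the stated power) | 0.805 | 0.762 |
| Chi-square, continuity-corrected | 0.787 | 0.743 |
| Normal approximation | 0.831 | 0.797 |
| Mid-p | 0.857 | 0.824 |
| Chi-square, uncorrected | 0.864 | 0.829 |

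Only the exact version gives 0.80516 at 61.

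**Step 7: check the corrected enrolment.** 88 × 0.70 = 61.6 expected pairs, which meets the 61 required; 87 × 0.70 = 60.9 does not.

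**The case against.** The strongest reply is that the loss is conditional and small. The 80.5% in the table is attached to 61 pairs, where it is correct, and the document states no power for 80 enrolled. The 30% is a planning allowance given without a source. If fewer than about 24% drop out, 80 is enough; if nobody does, exact power at 80 pairs is 0.908. Section 14 does not commit to the exact test, and with the mid-p or uncorrected chi-square version power at 56 pairs stays above 80%. Drop-out is not defined, so counting every drop-out as a lost pair is an assumption. Finally, five pairs matter less than the fragility of the pilot inputs. Moving one pilot patient to P10 = 0.20 with P01 = 0.05 gives exact power of 0.590 at 61 pairs; P10 = 0.25 with P01 = 0.10 gives 0.432.

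Most of this stands as a limit on the size of the problem. The shortfall does depend on losing the full 30%, and the fall below 80% is shown for the exact calculation, not for every version of the test. None of it reconciles the three figures, since no choice of test makes 70% of 80 equal 61. The exact calculation is the one the plan used to justify 61, so it is the fair basis for judging whether the enrolment delivers what was claimed. If a lower drop-out rate is thought realistic, Section 7-4 should state that rate. The pilot uncertainty is a separate matter and does not correct this step.

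**Conclusion.** The drop-out statement in Section 7-4 is wrong as written. At the plan's own 30% drop-out, 80 enrolled patients leave 56 pairs, 5 short of the 61 required. On the plan's own exact calculation, power is then 76.2% instead of 80.5%. Eighty patients support at most 23.75% drop-out; 30% would need 88.

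The arithmetic rests on two assumptions: that the full 30% is lost, as the plan assumes, and that each drop-out costs one pair, which follows from the paired design with no stated handling of incomplete pairs. The power figure also rests on the exact two-sided test and the pilot proportions of 0.25 and 0.05. The loss is modest, and the 61-pair calculation is sound.

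**What to change.** Correct the last clause of the sample-size sentence in Section 7-4, in one of two ways.

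- **Keep 80 and restate what it covers.** Say that 80 enrolled patients provide at least 61 pairs with drop-out of up to about 23% (19 of 80), and that at 30% drop-out 56 pairs remain, with power of about 76% by the two-sided exact McNemar calculation.
- **Keep 30% and restate the number.** Give 61 / 0.70 = 87.1, rounded up to 88, and show the formula.

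The first option is sufficient. It costs one sentence and no extra patients, and its only price is a slightly less favourable claim about drop-out tolerance or power. The second adds 8 patients to the target.

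### The plan does not say which McNemar test it will use, and the stated 80% power does not hold at the 56 pairs its own drop-out assumption leaves

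*Combined protocol and SAP*

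**What the plan says.** Section 14 (Data and Statistical Analysis) states that the success rates of the two methods, each used once in the same patient, are "analyzed using the McNemar test". It does not say whether the test is exact, mid-P, uncorrected chi-square or continuity-corrected chi-square. It also plans no paired difference or confidence interval for the primary comparison.

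Section 7-4 takes its inputs from a pilot of 20 patients, with "5 cases of success only with Kara-hoc" and "only 1 case of success with conventional method", hence "with a difference of 20" percentage points. It concludes that "a total of 61 cases were required" and that "80 cases were required when the drop-out rate of 30% was taken into account". The output table, headed "Numeric Results for Two-Sided Test", gives power 0.80516 at N = 61 with alpha 0.050. It does not name the form of the test either.

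**The concern.** The forms of the McNemar test differ noticeably when few pairs are discordant. With 56 pairs and 30% discordance, about 17 discordant pairs are expected (56 x 0.30 = 16.8), and the forms can then disagree about significance. A 13 to 4 split gives p = 0.049 with the exact test but 0.052 with the continuity correction. A 12 to 4 split gives 0.077 with the exact test but 0.049 with mid-P. If the form stays open, it can be chosen after the data are seen.

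The second problem is the power figure itself. It belongs to 61 completed pairs, but the plan's enrolment and drop-out do not deliver 61. The trial therefore relies on a stated 80% that its own assumptions do not support under the test that produced it.

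**Working it through.** **Inputs, all from Section 7-4.** P10 = 5/20 = 0.25, P01 = 1/20 = 0.05, discordance 0.30, difference 0.20, two-sided alpha 0.05, 61 pairs required, 80 enrolled, 30% drop-out.

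**Step 1: reproduce the stated power.** The number of discordant pairs m follows Binomial(N, 0.30). Given m, the number favouring the new device, b, follows Binomial(m, 0.25/0.30). Power is the total probability of all (m, b) for which the test gives p <= 0.05. For the exact test, p is the two-sided binomial p-value for b out of m at 0.5. For mid-P, p is that value minus the probability of the observed b.

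At N = 61 the exact form gives 0.80516, equal to the table to five decimals; N = 60 gives 0.797. No other form matches at N = 61: continuity-corrected 0.787, mid-P 0.857, uncorrected 0.864. That the exact form was used is inferred from this match; the plan does not say so.

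**Step 2: the drop-out allowance.**

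- As planned: 61 x 1.3 = 79.3, rounded up to 80.
- Pairs left after 30% loss: 80 x 0.70 = 56.
- Enrolment needed to keep 61: 61/0.70 = 87.1, rounded up to 88.

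**Step 3: power and type I error.** Type I error is enumerated the same way with P10 = P01 = 0.15. The last column is the maximum over all discordance rates at 56 pairs.

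| Form | Power, 61 pairs | Power, 56 pairs | Type I error, 56 pairs, 30% discordance | Maximum type I error, 56 pairs |
|---|---|---|---|---|
| Exact | 0.805 | 0.762 | 2.9% | 4.4% |
| Continuity-corrected | 0.787 | 0.743 | 2.5% | 4.4% |
| Mid-P | 0.857 | 0.824 | 4.7% | 5.02% (near 88% discordance) |
| Uncorrected | 0.864 | 0.829 | 5.0% | 5.4% (near 44% discordance) |

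Under the exact test, going from 61 to 56 pairs costs 0.805 - 0.762 = 4.3 points. At 56 pairs, mid-P gains 0.824 - 0.762 = 6.2 points over exact. Mid-P first reaches 80% at 53 pairs (0.801), against 61 for exact.

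**Step 4: unused error of the exact test.** At 30% discordance its size is 0.0294 with 61 pairs and 0.0288 with 56. The unused share is 1 - 0.0294/0.05 = 41% and 1 - 0.0288/0.05 = 42%.

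**Step 5: dependence on the pilot.** The inputs rest on six discordant pairs. At 56 pairs:

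| P10 / P01 | Exact power | Mid-P power |
|---|---|---|
| 0.25 / 0.05 (planned) | 0.762 | 0.824 |
| 0.20 / 0.05 | 0.541 | 0.631 |
| 0.25 / 0.10 | 0.398 | 0.472 |
| 0.30 / 0.10 | 0.601 | 0.668 |

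**Step 6: precision of the paired difference.** The paired standard error at the planned effect is sqrt((0.30 - 0.20²)/N). At 61 pairs this is sqrt(0.26/61) = 0.0653, a 95% half-width of 12.8 points. At 56 pairs it is sqrt(0.26/56) = 0.0681, a half-width of 13.4 points.

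**The case against.** The best case for leaving the test alone is that the exact McNemar test is valid. It holds the 5% level at every discordance rate, and it is the form that matches the sample size. Conservatism is the price of that guarantee. The smallest repair would be to add the word exact to Section 14. Mid-P would replace it with a test on which the sample size was not based and whose error can slightly exceed 5%. This stands as far as it goes: choosing mid-P is an efficiency gain, not the correction of an invalid test. It does not rescue the power figure, because naming the exact test still leaves 0.762 at 56 pairs.

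A reader might also infer more than the documents support:

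- That the exact test throws away half of the 5%. At the planned discordance it leaves 41 to 42% unused; just over half is unused only if discordance is near 20%.
- That the trial will end with 56 pairs. This is a projection. If no more than 19 of the 80 are lost (24%), at least 61 pairs remain and the exact test keeps its 80%.
- That mid-P alone keeps 80% at 56 pairs. The uncorrected chi-square does so too, at 0.829, with the weaker error control shown above.
- That the plan would use an unpaired interval. Nothing calls for one, and Section 14 relies explicitly on each patient having both methods. The supported point is only that no paired estimate is specified.

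Finally, mid-P offsets the drop-out shortfall at the planned effect but does not correct the inflation step, which needs its own correction.

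**Conclusion.** The point holds on two levels. The power statement is wrong as written: under the test that reproduces it, and with the plan's own enrolment and drop-out, power is 0.762 rather than 0.805. The unnamed form of the test is a cheap improvement rather than an error. At 56 pairs the choice spans 0.743 to 0.829, and mid-P restores 80% while keeping its type I error at or below 5.02%.

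These figures assume that the 30% drop-out occurs, that P10 = 0.25 and P01 = 0.05 are true, and that the exact form lay behind the table. The second assumption is the most fragile: the alternatives tried bring mid-P power at 56 pairs down to between 0.47 and 0.67, so neither form secures 80% if the pilot was optimistic.

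**What to change.** In Section 7-4, correct the drop-out statement: 80 enrolled with 30% loss leaves 56 pairs, and keeping 61 would need 88. Give the power at 56 pairs, which is 0.824 if mid-P is adopted or 0.762 if the exact test is kept, and note that it rests on six discordant pilot pairs.

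In Section 14, before any data are seen, specify:

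- the two-sided mid-P McNemar test at 0.05 as the primary test;
- the exact McNemar p-value as a sensitivity result;
- the paired difference in success rates (new device minus conventional) with a 95% confidence interval for paired proportions.

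The cost is a few sentences and no additional patients if enrolment stays at 80; raising it to 88 would add eight. The downside is that mid-P does not strictly guarantee 5%. Its worst case at 56 pairs is 5.02%, at a discordance far above the planned 30%. A sponsor who wants strict control can name the exact test instead and restate the power as 0.762.

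### Section 14 names only logistic regression for success factors, without a unit of analysis or a method for the two punctures per patient; pooled as independent records, standard errors are wrong unless residual within-patient correlation is zero

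*Combined protocol and SAP*

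**What the plan says.** Section 6 lists the factors for a successful puncture as secondary purpose d. Section 9 does not repeat it among the secondary evaluation items, which are "Occurrence of surgical complications, patient satisfaction, operator satisfaction, number of re-punctures". Section 21 says that personal data are collected for "analyzing all patients to find out what factors cause a significant difference during ascites puncture", and lists "gender, date of birth, height, weight, disease name, past medical history, and blood test findings".

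The outcome belongs to the puncture. Section 10 defines it as "Multiple puncture success : Drainage of 3L or more per puncture". Under Section 9 patients "perform Karahoc puncture and vascular catheter puncture once each", in random order, and the clinical trial schedule marks "Confirmation of puncture success" at both session 1 and session 2. No section defines success at patient level.

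Section 14 uses this pairing for the primary test, on the ground that the comparison "is a procedure that is repeated once in the same patient". For the factor analysis it then says: "Multivariate analysis is performed using logistic regression for factors involved in treatment success in the entire patient group". The closing phrase names a population, not a record unit. No random effect, generalised estimating equation (GEE), conditional model or cluster-robust variance is mentioned, and no rule reduces two outcomes to one per patient.

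**The concern.** Ordinary logistic regression treats every record as independent. If both punctures of a patient are stacked as two records, a factor such as sex, height or medical history takes the same value twice, beside two outcomes from the same abdomen. If those outcomes remain positively correlated after adjustment, the data hold less information about such a factor than the model assumes. Its standard error is then too small, and chance factors are reported as success factors more often than the nominal rate. With negative correlation the standard error is too large. The plan recognises the pairing in one sentence and does not carry it into the next.

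**Working it through.** **The plan's own figure.** Section 7-4 gives no figure for the regression, only for McNemar: power 0.80516 at N = 61 with P10 = 0.25, P01 = 0.05 and two-sided alpha 0.05. Taking the exact test on m discordant pairs, with m ~ Bin(61, 0.30) and a Kara-hoc share of 0.25/0.30, and averaging over m, gives 0.80516. The figure is reproduced, and nothing below changes it.

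**Within-patient correlation from the pilot (Section 7-4).** Of 20 patients, 12 succeeded with both devices, 5 with Kara-hoc only and 1 with the conventional method only. By subtraction, 20 - 12 - 5 - 1 = 2 succeeded with neither.
- Success rates: 17/20 = 0.85 and 13/20 = 0.65.
- Variances: 0.85 × 0.15 = 0.1275 and 0.65 × 0.35 = 0.2275. Their sum is 0.355 and the root of their product is 0.1703.
- phi = (0.60 - 0.85 × 0.65) / 0.1703 = 0.0475 / 0.1703 = 0.279.
- Bootstrap 95% range: about -0.21 to 0.69. This phi is adjusted for device only.

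**Factor constant within a patient, both punctures pooled.** True/ordinary variance = (0.355 + 2 × phi × 0.1703) / 0.355. Type I error = 2 × (1 - Phi(1.96 / SE ratio)), where the SE ratio is the root of the variance ratio.

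| phi | variance ratio | type I error |
|---|---|---|
| -0.2 | 0.808 | 2.9% |
| 0 | 1.000 | 5.0% |
| 0.14 | 1.134 | 6.6% |
| 0.279 | 1.268 | 8.2% |

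At 0.279 the SE ratio is 1.126, so the ordinary standard error is 1 - 1/1.126 = 11% too small.

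**Factor that varies between sessions.** With between-session correlation r, the excess shrinks in proportion: variance ratio = 1 + r × 0.268. With r = 0.5, an assumption because the documents give no value, this is 1.134, or 6.6%. With r = 0 it is 1, or 5.0%.

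**Device term.** Per patient, the ordinary variance of the log odds ratio is 1/0.1275 + 1/0.2275 = 12.24. The pairing removes 2 × 0.279/0.1703 = 3.28, which leaves 8.96. The SE ratio is √(8.96/12.24) = 0.86, so the ordinary standard error is too large.

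**Simulation.** 61 patients, two sessions, success 0.85 and 0.65, null patient-constant factors plus device and session, 10,000 runs per setting. Type I error per factor:

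| Factors | Method | phi 0 | phi 0.28 |
|---|---|---|---|
| 1 | ordinary logistic | 4.8% | 8.0% |
| 3 | ordinary logistic | 5.2% | 8.3% |
| 7 | ordinary logistic | 5.5% | 9.1% |
| 1 | GEE, Kauermann-Carroll | 4.5% | 4.7% |
| 3 | GEE, Kauermann-Carroll | 5.1% | 5.0% |
| 7 | GEE, Kauermann-Carroll | 5.2% | 5.1% |
| 7 | GEE, no correction | 7.4% | 7.4% |

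Smaller runs at phi 0.28 with r = 0.5 gave 6.7% with three factors and 7.2% with seven. Simulated SE ratios for the device term were 0.86 to 0.88. The factor counts are assumptions: the plan names no model terms, and seven mirrors the kinds of information in Section 21.

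**The case against.** The strongest objection is that the plan never says it will pool. Sections 14 and 21 both speak of patients. One record per patient, or one model per device, would also fit the words, and neither has a clustering error. This stands: a reader might infer that the plan prescribes an invalid analysis, and the text does not go that far. Against it, success exists only per puncture and no patient-level outcome is defined, so pooling is the most natural reading. The choice of unit also matters in itself. At pilot rates a Kara-hoc-only model would rest on about 61 × 0.15 = 9 failures, and a pooled model on about 61 × 0.50 = 30.

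Second, a reader might apply the 8-9% to every candidate factor. The documents do not support that: the schedule repeats haematology, coagulation and biochemistry at sessions 1 and 2, so blood results can differ between a patient's two records. Also, the seven-factor figure is already 5.5% at zero correlation, so a little of the 9.1% is a small-sample effect and not clustering.

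Third, phi comes from 20 patients and its range includes zero and negative values. A reader might infer that standard errors are certain to be too small; the pilot does not settle even the sign. Positive correlation is plausible because the same abdomen is punctured twice, but it is an assumption. This limits the claim about size. It also favours a method that is valid for either sign.

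Finally, the analysis is exploratory. It is absent from the Section 9 evaluation items, and Section 7-4 sets alpha only for McNemar, so 5% here is a convention.

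**Conclusion.** The concern holds as a conditional one of minor severity. Section 14 leaves the unit of analysis and the handling of paired outcomes unstated. If both punctures enter as independent records, model-based standard errors are wrong unless the residual within-patient correlation is zero. If that correlation equals the pilot phi of 0.28:
- factors constant within a patient have a type I error of about 8-9% against a nominal 5%;
- factors that vary between sessions have about 6.5-7%, if their between-session correlation is assumed to be 0.5;
- the device term's true standard error is about 0.85-0.88 of the ordinary one, so that test is conservative.

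A reader might infer that the trial's main result is in doubt. It is not: McNemar's test already uses the pairing, and neither it nor its sample size is touched. Only the secondary factor analysis is affected.

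**What to change.** Replace the logistic regression sentence in Section 14 with wording such as: *Factors associated with success are analysed with one record per puncture by logistic regression with device and session as terms, accounting for the two punctures of each patient (for example GEE clustered on patient, with robust standard errors and a small-sample correction).*

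The essential parts are the record unit and the clustering on patient. The choice of correction is a preference: Kauermann-Carroll kept the error at 4.5% to 5.3% in the settings tried with 61 patients. A patient random intercept named in advance would also serve if the correlation is positive.

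The cost is analysis wording and slightly wider intervals for patient-level factors; the data are the same. Compared with ordinary logistic regression at 61 patients, Kauermann-Carroll standard errors are about 1.5% larger at phi 0 and 14% larger at phi 0.28 with one factor, and about 3.5% and 17% larger with seven. Most of the increase at phi 0.28 restores error that the ordinary model leaves out (true SE 12.6% larger, from the ratio of 1.126).
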